## 11.0 Data and Specimen Management

### 11.1 Analysis Plan.

#### Aim 1.

The proposed trial uses patient 1:2:2:2 randomization with random block size to achieve group comparability and balance. Stratified by clinic, each participant will be randomized to one of the four arms. The four arms are the result of a 2x2 factorial design, where SMS text reminder and portal are the two-level factors with all four arms receiving the EHR tools. We conservatively anticipate at least 80% retention for follow-up at six months. This will result in 1505 participants recruited to the study with an anticipated minimum of 1204 (172 participants in EHR arm and 344 per the other arms) available after six months, contributing to primary data analysis. Due to an NIA administrative hold, the interventions were not implemented as planned. Hence it was determined that the primary analysis would be “per-protocol” rather than intent-to-treat to assess the effect of the interventions under optimal conditions. Participants who received the initial 6 weeks of SMS messaging continuously will be considered as receiving the SMS intervention, and participants who logged on to the patient portal and completed at least one survey will be considered as receiving the patient portal.

To ensure adequate balance across treatment arms, baseline outcomes and potential confounders including socio-demographic characteristics, comorbidities, regimen complexity (i.e. # of medications, total pills taken daily), health literacy level, and language will be examined. Variables found to have clinically meaningful differences across treatment groups will be entered as covariates in the generalized linear mixed models (GLMMs) used for formal analyses as described below.

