Prescription medication adherence at 6 months is the primary outcome of interest for Aim 1, with treatment knowledge regimen consolidation, and clinical outcomes being relevant to hypotheses of secondary interest. We will use generalized linear mixed-effects models (GLMMs) to test for the effects of SMS text reminder and Portal, specifying the proper link functions based on the distribution of the outcome variable. Analyses will be performed using PROC GENMOD in SAS (v.9.4). SMS text reminder and Portal (both binary) and an interaction term for SMS and Portal are the three variables included in the model to denote the intervention groups and the enhanced usual care group (H1-6). Since adherence will be assessed for each medication, 2-level GLMM will be used with medications nested in participants. We will test for differences in the outcomes between each of the groups and the enhanced usual care arm to determine benefits of SMS texting or portal use, or both by constructing contrasts.

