#### Aim 2.

We will determine the extent to which the interventions were implemented as planned (a process evaluation) across each of the sites and for all four study arms. We will collect EHR data on prescriptions and end of visit summaries to assess whether patients actually received new prescription orders (in after visit summaries) with the

UMS sigs, and review pharmacy records to determine if they were translated accordingly onto patients' drug container labels. We will also observe during patient interviews (that occur after medical encounters) which patients received the MedSheets and MedList. For those receiving SMS text reminders (SMS and SMS+Portal arms), we will ask patients at all follow-up intervals whether they received the text messages. For those electing to turn off the service, we will qualitatively explore and code reasons why. For patients who receive the Portal (Portal and SMS+Portal), we will track usage data, rate of entry errors, review technical support logs for the frequency and nature of calls, and also investigate at each follow-up patient satisfaction, acceptability and usability of the portal.

Aim 3.

We will directly measure and assess the perspective costs of developing and running UMS interventions, alone and in combination. Specifically, we will estimate the incremental cost of interventions relative to usual care from the perspective of the Alliance, Erie, and Northwestern. The primary costs of running UMS technologies involves the limited expenses around printing (printer ink, paper, staff time) as a result of generating new Rx information with after-visit summaries. SMS monthly costs will be easily documented as well as usage. However, we will include estimates for programming maintenance, for both GE Centricity EHR/Epic and the patient portal, and will test the sensitivity of results to changes in the maintenance requirements in terms of programmer hours. We also will separately track development costs for software and other programming requirements based on programmer hours. Staff/programmer costs will be measured using tracked time spent on the intervention and wage estimates. We will test the sensitivity of operational costs to different assumptions about the potential use of variable staff using different salaries but assuming the same proficiency in terms of time required. Further, we will assess the sensitivity of estimates to different proficiency levels that could arise from learning by doing.

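### The only primary comparison is per-protocol, with receipt set after randomisation; no as-randomised analysis is named, and the stated N and power belong to the randomised arms

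*Combined protocol and SAP*

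**What the plan says.** Section 11.1, Aim 1, gives the reason for the change: "Due to an NIA administrative hold, the interventions were not implemented as planned". The primary analysis is therefore per-protocol "rather than intent-to-treat to assess the effect of the interventions under optimal conditions".

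Receipt is defined by two rules:
- SMS: "Participants who received the initial 6 weeks of SMS messaging continuously will be considered as receiving the SMS intervention".
- Portal: "participants who logged on to the patient portal and completed at least one survey will be considered as receiving the patient portal".

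The model description in Aim 1 states that "SMS text reminder and Portal (both binary) and an interaction term for SMS and Portal are the three variables included in the model". It does not say whether these terms code assignment or receipt. Adjustment depends on observed imbalance: "Variables found to have clinically meaningful differences across treatment groups will be entered as covariates".

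The same section counts "172 participants in EHR arm and 344 per the other arms) available after six months, contributing to primary data analysis". Section 11.2 uses those group sizes, 69% adherence under enhanced usual care and a 2.5% type 1 error rate to claim 80% power for a 12-point difference.

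The Exploratory Analyses add dose response, covariate interactions and a comparison of adherence measures. Intent-to-treat is mentioned only as the approach that was replaced.

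**The concern.** Both receipt rules are settled after randomisation and are partly in the patient's hands. Section 9.14 lets patients stop the texts at any time, and Aim 2 provides for this: "For those electing to turn off the service, we will qualitatively explore and code reasons why". Section 9.15 requires the patient to complete the portal survey. Patients who keep the texts running or answer surveys may differ in adherence from those who do not, and adherence is the outcome. Enhanced usual care has no receipt condition, so in H1 and H2 a selected group is compared with an unselected one.

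Aim 1 in section 1.1 concerns effectiveness, and H1 and H2 in section 1.2 name study arms. Delivery problems justify adding a per-protocol analysis. They do not justify dropping the comparison that randomisation protects. Adjusting for measured variables that happen to look imbalanced removes only part of any selection.

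Two further gaps follow. Excluding non-receivers and recoding them by what they received give different datasets, and the text fits either. The sample size and power are presented as those of the primary analysis, yet they hold for it only if every retained participant meets the receipt rule. Followed as written, the plan could report an effect created by selection, or miss a real one, with no randomised result beside it.

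**Working it through.** **Inputs from the plan.** 1505 enrolled, 80% retention and 1:2:2:2 allocation (11.1); 69% control adherence, a 12-point difference and 2.5% type 1 error (11.2). Sidedness is not stated; two-sided is assumed because it comes closest to the stated power.

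**Assumed, because the documents give no figure.** Receipt f = 0.8, 0.6 or 0.4, the same for both interventions; a 10 to 20 point adherence gap g between receivers and self-selected non-receivers.

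**1. The plan's own figures.** 1505 × 0.80 = 1204 = 172 + 3 × 344. No receipt term enters.

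Power = Φ[(d − z·SE₀)/SE₁], with z = 2.241, SE₀ pooled and SE₁ unpooled. For 172 v 344 and 0.69 v 0.81: SE₀ = 0.0393, SE₁ = 0.0411, so (0.12 − 0.0881)/0.0411 = 0.776 and power = 78.1%. The detectable difference at 80% power is 12.2 points. This agrees with the plan for the randomised arms with full delivery.

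**2. H1/H2 under each reading of the per-protocol rule, and as randomised.**

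| Receipt f | 0.8 | 0.6 | 0.4 |
|---|---|---|---|
| Exclusion: receivers, 344f | 275 | 206 | 138 |
| Exclusion: power | 74% | 68% | 57% |
| Exclusion: detectable difference (points) | 12.7 | 13.5 | 15.0 |
| Recoding, independent receipt: nominal power | 91% | 93% | 91% |
| Recoding, fully correlated receipt: nominal power | 90% | 88% | 76% |
| As randomised, effect 0.12f: power | 56% | 32% | 14% |

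Recoded cells with independent receipt: none = 172 + 688(1−f) + 344(1−f)² = 323/502/709; each single = 344f + 344f(1−f) = 330/289/220; both = 344f² = 220/124/55. With fully correlated receipt: none = 172 + 1032(1−f) = 378/585/791; each other cell = 344f = 275/206/138. Each set totals 1204 before rounding.

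**3. H3/H4 under exclusion.** The combination cell is 220/124/55 (independent) or 275/206/138 (fully correlated) instead of 344. With the comparator at an assumed 81%, the detectable difference is 9.8/12.0/16.0 or 9.2/10.4/12.4 points, against 8.3 at full receipt. With the comparator at 69% it is 12.1/15.0/20.3 or 11.4/13.0/15.6, against 10.3.

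**4. Selection bias with no true effect, f = 0.6, no adjustment.**
- *H1/H2, exclusion.* Bias = g(1 − q), where q = f/[1 − (1−f)(1−s)] and s is the self-selected share of non-receipt. With s = 1, q = 0.6 and the bias is 4 to 8 points; with s = 0.5, q = 0.75 and it is 2.5 to 5; with s = 0 it is zero. For s = 1, 172 v 206, false rejection at a nominal 2.5% is 8 to 31% if receivers are more adherent (0.69 v 0.73 to 0.77) and 8 to 27% if they are less adherent (0.69 v 0.65 to 0.61).
- *A true 12-point effect with that downward bias.* Power falls from 68% to 31% (0.69 v 0.77) or 8% (0.69 v 0.73).
- *H1/H2, recoding, s = 1.* Take deviations from the arm mean. With independent, additive selection, the single cell averages (206.4 × 0.4g − 82.56 × 0.2g)/288.96 = 0.229g and the none cell −(275.2 × 0.6g + 55.04 × 1.2g)/502.24 = −0.460g. The bias is 0.689g, or 6.9 to 13.8 points. With fully correlated receipt it is 0.4g + 412.8 × 0.6g/584.8 = 0.824g, or 8.2 to 16.5 points.
- *H3/H4, exclusion, s = 1.* Selection on the shared factor largely cancels. What remains is selection on the added factor: g(1−f) = 4 to 8 points if receipt is independent, zero if fully correlated.

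**The case against.** The change is disclosed, it has an external cause, and the target is named as the effect under good delivery. The text settles which analysis is primary; it is silent on an as-randomised secondary analysis and does not reject one. H3 and H4 describe the tested group as patients receiving both interventions, which is receipt wording. Aim 2 already evaluates implementation across all four arms, section 8.1 plans for text opt-out and portal login data, and Aim 1 includes some covariate adjustment.

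The sizes above rest on assumed receipt rates, gaps and correlations. A single receipt rate is crude when one rule needs six unbroken weeks of texts and the other only one of six surveys. The check is a participant-level two-proportion test, whereas Aim 1 plans a model with medications nested in participants. The as-randomised analysis could have low power.

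Most of this stands as a limit on size, and reporting of non-receipt is partly planned already. None of it supplies a randomised comparison or says what happens to non-receivers. Low power in the as-randomised analysis calls for cautious reading of a null result, not for leaving the analysis out.

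**Conclusion.** The concern holds. As written, all four hypotheses rest only on groups defined by post-randomisation receipt, and the handling of non-receivers is undefined. The power arithmetic is correct for the randomised arms; the fault is that it is attached to a different analysis set. It does not follow that power is below 80%: at the assumed receipt rates exclusion lowers it, while recoding mostly raises it nominally, on groups that are no longer randomised.

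The size cannot be fixed from the documents. In the 60% scenario with exclusion, H1/H2 bias runs from zero (the hold caused all non-receipt at random) to 4 to 8 points in either direction (all self-selected). If adjustment removed half the selection, the bias would be half as large. The missing randomised comparison is the serious part and should be corrected before analysis.

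**What to change.** 1. **Section 11.1, as-randomised analysis.** Add an analysis of H1 to H4 with participants in their assigned arm, and report it beside the per-protocol result. State that it is a completer analysis if only retained participants enter. Describe the per-protocol result as the effect under receipt, not as the randomised effectiveness comparison.
2. **Section 11.1, per-protocol rule.** State whether non-receivers are excluded or recoded, and what receipt the combination group needs. Adjust for baseline adherence and the confounders already listed in Aim 1, whether or not they look imbalanced. Report non-receipt by arm, building on Aim 2, and use the opt-out data in section 8.1 to separate SMS opt-out from non-delivery due to the hold as far as the records allow.
3. **Sections 11.1 and 11.2, N and power.** State that 1204, 80% and 12 points refer to the randomised arms with full delivery. Give the detectable difference for the per-protocol set over a range of receipt, separately for H1/H2 and H3/H4.

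Optional: a complier average causal effect with assigned arm as instrument, noting that partial receipt may violate the exclusion restriction; and, if hold dates are available, a sensitivity analysis restricted by hold date identically in all arms.

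**Cost.** SAP wording and a few extra model runs on data already planned. Section 9.14 keeps patients who stop the texts in the study, so their outcomes should be available. The drawback is the dilution shown above: as-randomised power for H1/H2 of 56/32/14% at 80/60/40% receipt if only receivers gain 12 points.

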## 8.0 Study Endpoints

### 8.1 Covariates.

Patient characteristics: Socio-demographic characteristics, language, country of origin, time in US, comorbidities, social support, cognition (the cognitive assessment will not be completed if the baseline interview is completed over the phone), and health status will be collected. A literacy assessment using the Newest Vital Sign (NVS) and brief health literacy screener, and the Consumer Health Activation Index (CHAI) will be administered.

Regimen characteristics: Rx drugs will be collected and grouped into drug class. Regimen complexity will be calculated via the Medication Regimen Complexity Index (MRCI).

Provider-Patient Prescription Communication: We will ask questions adapted from the Consumer Assessment of Health Providers Survey (CAHPS-modified only as

necessary) to evaluate the extent and quality of provider verbal counseling on prescription medications.

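### The covariates of the primary per-protocol model depend on an undefined imbalance rule, and clinic, the randomisation stratum, is not among the named terms or candidates

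*Combined protocol and SAP*

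**What the plan says.** Section 11.1, Aim 1, describes the allocation: "Stratified by clinic, each participant will be randomized to one of the four arms". It then makes a per-protocol analysis primary, because an administrative hold kept the interventions from being delivered as planned. Receipt of SMS means six continuous initial weeks of messages. For the portal, "participants who logged on to the patient portal and completed at least one survey will be considered as receiving the patient portal".

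The balance check begins "To ensure adequate balance across treatment arms, baseline outcomes and potential confounders" and gives an open list: socio-demographic characteristics, comorbidities, regimen complexity (medication and daily pill counts), health literacy and language. The entry rule follows: "Variables found to have clinically meaningful differences across treatment groups will be entered as covariates in the generalized linear mixed models (GLMMs".

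The model paragraph of Aim 1 says that SMS, Portal and their interaction "are the three variables included in the model to denote the intervention groups and the enhanced usual care group". Its two levels are medications and participants. Clinic appears neither there nor in the candidate list.

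Section 8.1 defines regimen complexity differently: "Regimen complexity will be calculated via the Medication Regimen Complexity Index (MRCI". It also lists baseline variables to be collected, without committing any of them to the primary model.

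**The concern.** Three things are left open in the primary model.

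- **The cut-off.** A variable enters if its difference is judged clinically meaningful. No metric, threshold or decision-maker is named, so the model is not fixed before the data are seen.
- **The grouping.** The stated aim is balance across arms, while the rule refers to treatment groups. The primary contrast is by receipt. If randomised arms are screened, imbalance between the groups actually compared is not examined.
- **Clinic.** The two health systems use different portals (section 9.15) and may serve different populations (section 20.2 gives Erie as 85% Latino), so uptake may differ by clinic. If it does, stratified allocation no longer balances clinic in the receipt comparison.

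In an analysis as randomised this would be mainly a matter of precision and transparency. Here covariate adjustment is the only protection against confounding that section 11.1 states, so the primary estimate depends on choices not yet made.

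**Working it through.** **The plan's own figure.** Section 11.2 gives 172 and 344 analysable participants, 69% adherence in enhanced usual care, a 12-point difference, a type I error of 2.5% (taken as two-sided) and 80% power.
- Pooled rate: (172×0.69 + 344×0.81)/516 = 0.770.
- Null SE: √(0.770×0.230×(1/172 + 1/344)) = 0.0393.
- Alternative SE: √(0.69×0.31/172 + 0.81×0.19/344) = 0.0411.
- Power: Φ((0.12 − 2.241×0.0393)/0.0411) = 78.1%. The figure reproduces to within 2 points, and covariate adjustment does not alter the planned 1505.

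**Assumptions for the rule.** None of these is in the documents. There is no true effect. Six baseline covariates each differ by 0.1 SD in receivers, and each has correlation r of 0.1 or 0.2 with a latent normal adherence score. There is one binary outcome per participant. Groups are 172 and 344.

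**Hand check (independent covariates, all shifted the same way).** A standardised difference has mean 0.1 and SE √(1/172 + 1/344) = 0.0934.
- With a 0.2 SD cut-off, each covariate enters with probability 0.143, or 0.86 of six on average. The mean shift left unadjusted is 0.0649 SD per covariate.
- At r = 0.2 the latent shift is 6×0.0649×0.2 = 0.078. The spurious effect is Φ(0.496 + 0.078) − 0.69 = 2.7 points.
- With a 0.1 SD cut-off the remaining shift is 0.0149 SD per covariate, which gives 0.6 points.

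**Simulation, 10,000 trials per row.** Entries are bias in points, with type I error in % (nominal 2.5) in brackets.

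| Covariates | r | None entered | 0.2 SD rule | 0.1 SD rule | All entered |
|---|---|---|---|---|---|
| Independent, same direction | 0.1 | 2.1 (4.4) | 1.4 (3.4) | 0.3 (2.7) | 0.0 (2.8) |
| | 0.2 | 4.0 (10.5) | 2.6 (5.4) | 0.6 (2.3) | 0.0 (2.5) |
| Independent, 4 up, 2 down | 0.1 | 0.7 (2.7) | 0.5 (2.5) | 0.1 (2.5) | 0.0 (2.7) |
| | 0.2 | 1.4 (3.4) | 0.9 (2.7) | 0.2 (2.4) | 0.0 (2.6) |
| Correlated 0.3, same direction | 0.1 | 0.8 (2.7) | 0.3 (2.3) | −0.1 (2.3) | 0.0 (2.3) |
| | 0.2 | 1.6 (3.6) | 0.5 (2.4) | −0.3 (2.3) | 0.0 (2.4) |
| Correlated 0.3, mixed | 0.1 | 0.2 (2.6) | 0.0 (2.6) | −0.1 (2.6) | −0.1 (2.7) |
| | 0.2 | 0.5 (2.8) | 0.2 (2.5) | −0.1 (2.4) | 0.0 (2.5) |

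The least favourable case, with r = 0.2 on the observed binary scale, gives 3.4 points and 7.5%. The last column is near 0 by construction, because every simulated confounder is in the model.

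**Dependence on the cut-off.** In the same data set the two rules give estimates more than 1 point apart in 14% to 76% of null trials. The significance decision differs in 0.8% to 4.2%.

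**Screening randomised arms.** The expected arm difference is 0, so at 0.2 SD each covariate enters with probability 0.032, about 0.2 of six. With 60% receipt assumed (0.6×344 ≈ 206 receivers), the remaining bias over both cut-offs is 1.7 to 4.1 points (independent) or 0.5 to 1.6 (correlated 0.3).

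**Clinic left out altogether.** Assume two equal clinic groups whose adherence differs by D, with uptake u₁ and u₀, and receivers compared with enhanced usual care. Bias = D×(u₁/(u₁+u₀) − 0.5).
- Uptake 80% and 50%, D = 20 points: 20×(0.615 − 0.5) = 2.3 points.
- Equal uptake: 0.
- Extreme case, uptake 90% and 40%, D = 30 points: 30×(0.692 − 0.5) = 5.8 points.
- For groups as randomised there is no bias. The test is only conservative: at D = 20 points the SE is inflated by √(0.2139/(0.2139 − 0.1²)) = 1.024 and true alpha is 2.2%.

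**The case against.** The strongest reply is that the harm is small under plausible conditions. Section 2.1 itself ties age to multimorbidity, medication count, cognitive decline and limited literacy, so independent covariates are unlikely. With correlation 0.3, or with a 0.1 SD cut-off, bias is below about 0.7 points and type I error is near nominal. This stands.

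The group sizes are also open to challenge. The 344 is the whole retained arm, not a count of receivers. With 206 receivers, type I error in the same-direction case at r = 0.2 under the 0.2 SD rule falls to about 4% (3.6% and 3.7% in two runs), against 4.7% to 5.4% over repeated runs with 344. The planned model nests medications in participants, so these error rates do not transfer directly. This also stands.

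A reader might infer that receipt is simply patient self-selection. The documents do not support that: some non-receipt may come from the administrative hold, and the split is not given.

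A reader might also infer that a fixed covariate set should replace the screen. That can do worse than the plan. Suppose two confounders outside the set are each shifted 0.3 SD (an assumption) and the covariates are independent. The fixed set then leaves 2.0 to 3.9 points, against 1.4 to 2.8 under the 0.2 SD rule. Section 8.1 collects plausible variables of this kind, such as activation and social support.

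Finally, the three terms in Aim 1 denote the intervention groups and need not be the whole model, and the candidate list is open. Clinic could therefore be added, but nothing commits the analysis to it.

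**Conclusion.** The point holds as a gap in specification with a clear and cheap improvement. The covariate rule has no cut-off and no stated grouping, and clinic has no assured place in a comparison where stratified randomisation no longer guarantees its balance.

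The size cannot be derived from the documents, which give neither uptake nor adherence by clinic. Under the assumed scenarios the bias left by the rule is about 0 to about 3 points, or up to about 4 if randomised arms are screened. Type I error is close to 2.5% in most of them. It exceeds that mainly when covariates are independent, all shifted the same way, and the cut-off is loose. The clinic arithmetic is a separate illustration of a factor never entered; language, a listed candidate, may carry part of any such difference.

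Two stronger conclusions are not supported: that the rule is known to distort the result, and that omitting clinic would bias a comparison of the groups as randomised.

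**What to change.** In section 11.1, state that every primary contrast always includes:
- clinic, with small clinics pooled or clinic as a random effect if needed;
- the participant-level baseline value of the same adherence measure, where collected (for 24-hour recall, the share of the participant's drugs correctly dosed);
- age, sex, language, number of chronic conditions, health literacy (section 8.1 collects it: "A literacy assessment using the Newest Vital Sign (NVS) and brief health literacy screener"), and regimen complexity by one definition, the same in 8.1 and 11.1. The counts already in 11.1 can serve.

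Keep the imbalance screen only as an addition to this minimum. Apply it to the receipt groups actually compared, with a stated cut-off (for example an absolute standardised difference above 0.1), over the other baseline variables in 8.1, such as activation, social support and health status.

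Do not let missing baseline covariates remove participants; imputation from the other baseline variables is one way. Cognition is a poor candidate for the minimum set, because "the cognitive assessment will not be completed if the baseline interview is completed over the phone".

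State that the adjustment controls measured confounding only and does not make the per-protocol comparison equivalent to a randomised one.

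Cost: SAP wording, a few degrees of freedom (the number of clinics is not stated) and a little more analysis work. No new data are needed. If baseline 24-hour recall was not collected, that term is left out and the plan should say so. The change should be made before the final analysis, since afterwards the set would no longer be prespecified.
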